## 1.2 JUVENILE MYASTHENIA GRAVIS

Juvenile, or childhood, MG (JMG), defined by onset before the age of 18 years (O'Connell 2020) shares aspects of pathophysiology and most of the clinical features of adult early-onset MG (Gilhus et al. 2019). JMG is distinguished from genetic, non-autoimmune forms of neuromuscular transmission defect, the so-called congenital myasthenic syndromes.

The juvenile-onset and adult-onset MG differ with respect to epidemiology, frequency of ocular and generalized MG forms, prognosis, and therapeutic approaches.

A range of 12–80% of patients with JMG have been reported to have gMG (Chung et al. 2003; Kalb et al. 2002; Popperud et al. 2017), which is below the estimated frequency of 85% in adults. gMG is relatively uncommon in prepubertal children, regardless of race (Chung et al, 2003, O'Connell et al. 2020).

The pathophysiology of MG in pediatric patients is highly similar to that of adults. JMG is also caused by autoantibodies that bind to AChR or to other functionally relevant molecules in the postsynaptic membrane at the NMJ, such as MuSK or LRP4.

<sup>a Juvenile MG is not considered a separate subgroup and is part of early-onset MG. All patients at one time point can belong only to one subgroup.

<sup>b Ocular MG includes the patients with ocular symptoms only and no clinical weakness in other muscles.

However the percentage of patients seropositive for these molecules differ from adult-onset MG: majority of patients (90%) are AChR+, < 8% are MuSK+, and < 2% are LRP4+, whereas about 10%–30% of patients are seronegative (Finnis and Jayawant 2011; Takahashi et al. 2012; VanderPluym et al. 2013; Baraud 2018; Vecchio et al. 2020).

Diagnosis of JMG is established using the same evaluations and procedures as in adult MG.

### 1.3 CURRENT TREATMENT AND UNMET MEDICAL NEED

The goal of therapy in gMG is to induce pharmacological remission, complete stable remission, or minimal manifestations (MM), while minimizing side effects from medications (Jaretzki et al. 2000). The Myasthenia Gravis Foundation of America (MGFA) post-intervention status defines MM as a patient who has no symptoms or functional limitations from gMG but has some weakness on examination of some muscles. In October 2013, the MGFA appointed a Task Force, a panel of 15 international experts, who developed consensus-based guidance for the management of MG, which was published in 2016 (Sanders et al).

In contrast to adult MG there are no internationally accepted standards of care for JMG, and prospective randomized controlled data to evaluate treatment outcomes and efficacy have been difficult to collect. Most of the current practice on JMG diagnosis and treatment is extrapolated from adult trials and experience.

There are three types of primary therapies used to treat gMG:

- Symptomatic treatment using acetylcholinesterase (AChE) inhibitors (AChEls; anticholinesterases)
- Immunosuppressive and immunomodulatory therapies
- Thymectomy

Symptomatic treatment using AChEI increases the amount of acetylcholine available at the NMJ. Given its oral route of administration, pyridostigmine bromide is the preferred AChEI, and is usually the first-line medication in patients with gMG, including those with JMG. All subgroups of patients with gMG, with the exception of patients with MuSK+gMG, respond to AChEIs but with inter-individual variability in the degree of weakness relief, optimal dosage, and tolerability (Finnis and Jayawant et al. 2011; O'Connell et al. 2020). Muscle strength can be restored to normal levels over long periods in only a few patients with mild disease.

Chronic immunosuppressive therapies (glucocorticoids and non-steroidal immunosuppressive agents) target the underlying immune dysregulation. Patients with symptoms that exert functional impairment or reduce QoL when on maximum tolerated AChEI treatment should receive immunotherapy. Commonly used immunosuppressive therapies include oral corticosteroids (OCSs), antimetabolites (such as azathioprine,

mycophenolate mofetil, or methotrexate) and calcineurin inhibitors (such as cyclosporine and tacrolimus). The time of onset of clinical effect of each of these therapies for gMG varies considerably ranging from a few weeks for OCSs to approximately 2–12 months for mycophenolate mofetil and azathioprine (Sanders et al. 2016). The time of onset plays a large role, in addition to the pace and severity of the disease, in choosing the appropriate therapy for a given patient.

OCSs are first-line immunotherapy drugs for adult-onset and juvenile MG (O'Connell et al. 2020); in children, they are used cautiously, at the lowest possible dose because of growth retardation and other chronic systemic side effects, including weight gain, cushingoid features, hyperglycemia, hypertension, cataracts, glaucoma, behavioral changes, and susceptibility to infection.

Conventional steroid-sparing immunosuppressive agents are used on a limited basis in children because of the long-term risk of malignancy and teratogenicity (Munot et al. 2020); methotrexate, cyclosporine and cyclophosphamide are reserved only for refractory cases (see Section 4.5.3 for definition).

Patients with insufficient response, further disease worsening, or intolerance to the above medications may receive treatment with chronic IV immunoglobulin (IVIg), plasma exchange (PE), B-cell depletion with rituximab, or terminal complement activation inhibition with eculizumab (Soliris® U.S. Package Insert; Sanders et al. 2016). In single-arm study reports, rituximab was effective but with varying response rates (Anderson et al. 2016; Tandan et al. 2017; Robeson et al. 2017). Furthermore, in a Phase II trial in patients with AChR gMG (NCT02110706) rituximab was safe and well tolerated, but the study did not reach the primary endpoint of a 75% reduction in glucocorticoid levels. The use of rituximab in refractory JMG is sparsely documented (Zingariello et al. 2020; Barraud et al. 2018). Many of the therapies used in MG, including rituximab, are used off-label.

Therapeutic PE and IVIg are rapid but short-acting immunomodulating treatments. As such, they are typically used in patients with acute severe gMG when a rapid response is crucial, and are the mainstay of management of myasthenic crisis. As their effect is short-lived (4–12 weeks), maintenance immunotherapy is usually needed. They may be used as chronic, maintenance therapy in patients with refractory gMG (see Section 4.5.3 for definition) or in patients for whom immunosuppressive agents are relatively contraindicated, such as the pediatric population.

Thymectomy is indicated for patients with thymoma if resection is feasible and in many other AChR antibody–positive patients with non-thymomatous gMG who are 18–65 years old. In patients with a non-neoplastic thymus, thymectomy for the improvement of gMG has been performed for several decades, and is supported by extensive evidence on the pathogenetic role of the thymus in AChR + gMG and by a large number of studies showing a higher remission rate after thymectomy (Skeie et

al. 2010; Wolfe et al. 2016; Gronseth et al. 2020). The role and timing of thymectomy is still not well established or standardized in children. It is usually considered as a therapeutic option in AChR+gMG when the response to pyridostigmine and ISTs is incomplete or to avoid the long-term side effects of ISTs, especially corticosteroids. Thymectomy does not have an effect in MuSK gMG and has not been systematically examined in patients with gMG who have no detectable antibodies. Thymectomy does not cure gMG, and the long-term effect on antibody concentrations, T-cell subsets, and immune responses is very modest.

The majority of treated patients achieve a relatively stable condition allowing them to perform daily tasks (Andersen et al. 2016). However, only a few patients achieve remission, i.e., have no symptoms or signs of gMG and no evidence of weakness of any muscle on neurological examination. Even if fully functional, many patients experience side effects of the above listed treatments for gMG (Bacci et al. 2019). While children tend to exhibit higher rates of spontaneous or pharmacologic remission than adults, the frequency of refractory MG in pediatric population is unknown. OCSs, the most commonly used and fast-acting medications, result in a plethora of adverse effects that almost universally limit patients' QoL. Steroid-sparing agents are suboptimal alternatives because of their non-specific immunosuppressive profile, onset of action that may be delayed by more than 6 months, and significant long-term side effects, including malignancies. IVIg and therapeutic PE are associated with considerable logistical challenges. Overall, the unmet need in gMG remains high for disease-specific, more effective, safer, and relatively convenient treatments.

### 1.4 BACKGROUND ON SATRALIZUMAB

Satralizumab (RO5333787) is a humanized anti–interleukin-6 receptor (IL-6R) IgG2 monoclonal antibody that was constructed by modifying the amino acid sequence of tocilizumab to prolong its plasma drug-elimination half-life. In addition, satralizumab has the following distinguishing characteristics: pH-dependent binding to its antigen (IL-6R) (Igawa et al. 2010a), decreased antibody molecule isoelectric point (Igawa et al. 2010b), and stronger binding to neonatal Fc receptor (Petkova et al. 2006). Moreover, its Fc region has been modified to minimize antibody-dependent cellular cytotoxicity and complement-dependent cytotoxicity effector activity.

Satralizumab maintains pharmacological effects of IL-6R blockade using a 4-week dosing frequency by SC injection due to its prolonged plasma drug-elimination half-life. Satralizumab specifically targets the human IL-6R, preventing interleukin (IL)-6 from binding to the membrane-bound and soluble IL-6R (mIL-6R and sIL-6R respectively), thereby inhibiting IL-6 signaling.

The clinical pharmacology, safety, and efficacy of satralizumab has been characterized in four clinical trials: a single ascending dose (SA-001JP) trial in healthy subjects (both Japanese and Caucasian), a multiple ascending dose (SA-105JP) trial in patients with

rheumatoid arthritis (RA), and two Phase III clinical studies in patients with neuromyelitis optica spectrum disorder (NMOSD; BN40898 [SA-307JG] and BN40900 [SA-309JG).

Study BN40900 was a randomized (2:1 ratio), placebo-controlled trial in 95 patients without concurrent immunosuppressant (IST) therapy, and Study BN40898 was a randomized (1:1 ratio), placebo-controlled trial in 83 patients (76 adults and 7 adolescents, aged 12 to  $\leq$  17 years) using concurrent IST. All patients in Study BN40898 were receiving either concurrent azathioprine (34.9%), OCS (44.6%), or mycophenolate mofetil (14.5%) during the trial. Five adolescent patients received a combination of azathioprine or mycophenolate mofetil with corticosteroids. Meaningful and comparable efficacy based on relative risk of experiencing relapse was demonstrated in both Phase III studies in aquaporin-4 (AQP4) IgG–seropositive patients. The relative risk of experiencing an adjudicated relapse in AQP4-IgG–seropositive patients was reduced by 79% in Study BN40898 (N=55) and by 74% in Study BN40900 (N=64). Satralizumab 120 mg every 4 weeks (Q4W) given as monotherapy or in combination with IST was safe and well tolerated by patients with NMOSD.

Results from the Phase III clinical Studies BN40898 and BN40900 confirmed the adequacy of the selected dosing regimen (doses of 120 mg administered at Weeks 0, 2, and 4 followed by 120 mg Q4W). At this dose, the effective drug-elimination half-life is approximately 30 days based on data pooled between the two studies, supporting the recommended maintenance dosing interval of Q4W. Robust sIL-6R stabilization and increases in IL-6 levels were seen, indicative of target engagement. The median predicted occupancy at the sIL-6R and mIL-6R in patients with NMOSD was maintained at > 95% throughout the dose interval, and for the entire duration of therapy (Week 180 and Week 204 in Studies BN40898 and BN40900, respectively).

In Studies BN40898 and BN40900, anti-drug antibodies (ADAs) were observed in 41% and 71% of patients receiving satralizumab in the double-blind (DB) period, respectively. Apparent correlations between ADA development and higher body weight and lower exposure, were not reflected in clinical outcomes. Meaningful and comparable efficacy was demonstrated in all exposure subgroups and in all body weight groups.

During the Phase III studies BN40898 and BN40900 in NMOSD, satralizumab demonstrated a favorable safety profile. During the DB period, 63 patients were exposed to satralizumab monotherapy and 41 patients were exposed to satralizumab in combination with IST (please refer to the Satralizumab Investigator's Brochure for further details). In the DB period, patient median exposure to satralizumab was approximately two years in both studies. The median exposure to placebo was approximately one year.

Overall, satralizumab was well tolerated by patients with NMOSD. The safety profile of satralizumab in combination with OCS (15 mg of prednisolone equivalent per day), azathioprine or mycophenolate mofetil was comparable to satralizumab monotherapy.

The PK and safety profiles of satralizumab in adolescent patients was comparable to those in adult patients with NMOSD.

The most frequently reported adverse drug reactions were headache, arthralgia and injection reactions. The majority of adverse events were of mild or moderate severity and resolved without changes to the study drug. Injection reactions were reported in 12.5% of the patients treated with satralizumab (monotherapy or in combination with IST) and were predominantly of mild to moderate severity. The incidence rate of infections was not higher in the satralizumab group compared to the placebo group in both the monotherapy study (satralizumab: 99.8 events/100 patient years (PY) [95% CI: 82.4 to 119.8]; placebo: 162.6 events/100 PY [95% CI: 125.8 to 206.9]) and in the addon study (satralizumab + IST: 132.5 events/100 PY [95% CI: 108.2 to 160.5]; placebo + IST: 149.6 events/100 PY [95% CI: 120.1 to 184.1].

Laboratory abnormalities including neutropenia, thrombocytopenia, elevations in liver enzymes, and lipid elevations have been reported in patients treated with satralizumab.

Please refer to the Satralizumab Investigator's Brochure for details on nonclinical and clinical studies

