# 4.4.2.1 Medications Given with Precaution due to Effects Related to CYP Enzymes

No drug-drug interaction studies have been performed. Pop PK analyses did not detect any effect of azathioprine, mycophenolate mofetil, or OCS on the clearance of satralizumab.

Both in vitro and in vivo studies have shown that the expression of specific hepatic CYP450 enzymes (CYP1A2, CYP2C9, CYP2C19, and CYP3A4) is suppressed by cytokines such as IL-6. Modestly elevated IL-6 levels have been reported in patients with gMG.

Caution should be exercised when starting or discontinuing satralizumab treatment in patients who are receiving substrates of CYP450 3A4, 1A2, 2C9 or 2C19, particularly those with a narrow therapeutic index (such as warfarin, carbamazepine, phenytoin, and theophylline), and/or background ISTs (including tacrolimus and cyclosporine) and doses adjusted if needed.

Given the prolonged terminal half-life of satralizumab (approximately 30 days), the effect of satralizumab may persist for several months after stopping therapy.

The above lists of medications are not necessarily comprehensive. The investigator should consult the prescribing information when determining whether a concomitant medication can be safely administered with study treatment. In addition, the investigator should contact the Medical Monitor if questions arise regarding medications not listed above.

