# 5.3.1 Adverse Event Reporting Period

Investigators will seek information on adverse events at each patient contact.

All adverse events, whether reported by the patient or noted by study personnel, will be recorded in the patient's medical record and on the Adverse Event eCRF.

After informed consent has been obtained but prior to initiation of study drug, only serious adverse events caused by a protocol-mandated intervention (e.g., invasive procedures such as biopsies, discontinuation of medications) should be reported (see Section 5.4.2 for instructions for reporting serious adverse events).

After initiation of study drug, all adverse events will be reported until 12 weeks after the final dose of study drug.

Instructions for reporting adverse events that occur after the adverse event reporting period are provided in Section 5.6.

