4.5 SAFETY ANALYSES

The safety analysis population will consist of all randomized participants who received at least one dose of study drug, with participants grouped according to treatment and first dose received after randomization.

The main analyses will be done with a while on treatment strategy for two analyses sets: double-blind and overall satralizumab treatment period, which refers to the time in which participants are either randomized to satralizumab or switch to satralizumab at the beginning of the OLE period. The two analysis sets are defined as follows:

Analysis Set for the Double-Blind: All data up to the first dose in OLE, or up to 4 weeks after the last dose of the study drug (for participants who permanently discontinued the double-blind treatment), or last contact with the participant, or CCOD, whatever occurs first.

Analysis Set for the 'Overall Satralizumab Treatment': All data from the first dose of satralizumab (in the DB for the participants receiving satralizumab and in the **OLE for participants receiving placebo during the DB period**) until up to 4 weeks after the last dose of the satralizumab (for participants who permanently discontinued satralizumab), or last contact with the participant, or CCOD, whatever occurs first.

In addition, the data collected in the remaining period of the safety follow-up will be described separately and will use the analyses set for safety follow-up: all data later than 4 weeks after the last dose of study drug, for participants who permanently discontinued from the study drug.

Safety will be assessed through summaries of exposure to study treatment, AEs, changes in targeted laboratory test results, and changes in vital signs and electrocardiograms (ECGs).

Study treatment exposure (such as treatment duration, total dose received, and number of doses and dose modifications) will be summarized with descriptive statistics.

AE analyses will be performed on key subgroups including, but not limited to, age, race and region.

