4.5.2 Adverse Events

All verbatim AE terms will be coded using the Medical Dictionary for Regulatory Activities version that is current at the time of the analysis (AE intensity will be graded according to the National Cancer Institute Common Terminology Criteria for Adverse Events, version 5.0 (NCI CTCAE, v5.0) grading scale or according to Table 11 in Section 5.3.3 of the

Study Protocol (mild/moderate/severe/life-threatening/death), if the event is not specifically listed in the NCI CTCAE. For each treatment group, the frequency of each AE preferred term will be defined as the number of participants experiencing at least one occurrence of the AE. Each table will present the overall number of events and percentage of participants experiencing at least one AE.

Additional analyses for the 'overall satralizumab treatment' analysis set, summary of AE per 100 participant years will be provided. In this analysis multiple events will be counted each time they occur.

Percentages will be based on the number of participants in the safety-evaluable analysis population. In summary tables, AEs will be sorted by body system (in decreasing order of overall incidence), then by preferred term (in decreasing order of overall incidence).

The following safety information will be summarized by treatment group for the double-blind treatment period:

- AEs, AEs by intensity, AEs related to study drug
- Deaths
- Serious adverse events (SAEs), SAEs related to study drug
- AEs leading to discontinuation of study treatment
- AEs leading to dose modifications (dose interruption)
- Protocol-specified adverse events of special interest
- Infections
- Injection reactions.

The following data handling rules will be applied for all AE summary tables:

- Events that are missing both at onset and at end dates will be considered to have started after the first dose of study drug and the duration will be set to missing.
- If the onset date is missing, and the end date is on or after the first dosing date or unresolved or missing, then the event will be considered to have started after the first dose of study drug.

4.5.3 Laboratory Data

Laboratory data will be summarized by treatment group using descriptive statistics of absolute values and change from baseline values. In addition, the frequency of participants with abnormal laboratory values will be summarized by treatment group, visit, and baseline status.

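### For participants who stop treatment, adverse events more than 4 weeks after the last dose leave the randomised safety comparison, although the protocol collects them for 12 weeks

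*Protocol*

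**What the plan says.** SAP 4.5 makes the main safety analysis a while-on-treatment one with two data sets.

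- The double-blind (DB) set closes at the earliest of the first open-label (OLE) dose, last contact, the clinical cut-off or, for permanent discontinuers, "up to 4 weeks after the last dose of the study drug (for participants who permanently discontinued the double-blind treatment".
- The overall satralizumab set has the same 4-week limit after the last satralizumab dose.
- Beyond that limit, "the data collected in the remaining period of the safety follow-up will be described separately", in a third set holding "all data later than 4 weeks after the last dose of study drug, for participants who permanently discontinued from the study drug".

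SAP 4.5.2 opens its list of by-arm outputs with "The following safety information will be summarized by treatment group for the" double-blind treatment period. The list includes deaths, serious adverse events (SAEs), infections and adverse events of special interest (AESIs). SAP 4.1 and 4.5 group safety participants by the first treatment received after randomisation.

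The protocol uses a longer horizon. Section 5.3.1: "After initiation of study drug, all adverse events will be reported until 12 weeks after the final dose of study drug". Section 1.4 says that "the effective drug-elimination half-life is approximately 30 days" and that "The median predicted occupancy at the sIL-6R and mIL-6R in patients with NMOSD was maintained at > 95% throughout the dose interval". Section 4.4.2.1 adds that "the effect of satralizumab may persist for several months after stopping therapy", and 5.1.1.8 repeats this. Protocol 6.5, on safety analyses, sets no 4-week limit, and SAP Appendix 1 does not list one among its changes.

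**The concern.** Maintenance dosing is every 4 weeks, so day 28 after a dose is an ordinary trough. A participant who stops is therefore classed as off treatment at about the drug level that a continuing participant reaches just before each injection. Adverse events are then collected for up to eight more weeks but do not enter the by-arm tables. A death or serious infection five weeks after a DB discontinuer's last dose would be absent from the tables that compare the arms.

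Two features make this worth attention despite the small numbers. Discontinuers are a selected group: the protocol requires permanent discontinuation for some safety findings (Sections 4.6.1 and 5.1.1). And the events at issue are rare and serious, so one or two could change how a table reads.

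**Working it through.** **1. Who is affected.** Only permanent discontinuers. A completer entering the OLE is cut at the Week 24 dose, which is 4 weeks after the Week 20 dose.

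**2. Drug remaining.** With the protocol's 30-day half-life, the fraction left is 0.5^(days/30).
- 4 weeks: 0.5^(28/30) = 52%
- 8 weeks: 0.5^(56/30) = 27%
- 12 weeks: 0.5^(84/30) = 14%

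**3. Occupancy.** The figure above 95% cannot be reproduced, because the documents give no concentrations or binding constant. Nor do they give any occupancy beyond 4 weeks after a dose. As an illustration only, assume occupancy = C/(C+K), fixed at 95% at week 4 (C/K = 19), with first-order decline.
- Half-life 30 days: week 8, 19 × 0.524 = 9.96, so 9.96/10.96 = 91%; week 12, 19 × 0.274 = 5.21, so 5.21/6.21 = 84%.
- Half-life 15 to 40 days (assumed range): 84% to 92% at week 8, and 59% to 88% at week 12.
- Starting from 80% with a 30-day half-life (Protocol 3.4.1 reports a few patients predicted below 80%): 68% and 52%.

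**4. Check on the withdrawal rate.** SAP 2.2 assumes a difference of 2.0, SD 3.97, 85% power and 10% withdrawal. Per arm, 2 × (1.960 + 1.036)² × 3.97² / 2² = 70.8, so 71. Then 71/0.9 = 78.9, so 79 per arm and 158 in total, against 160 stated. The 10% is consistent with the plan's own sample size.

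**5. Person-time moved out of the DB comparison (upper limit).** Inputs are 185 participants, 1:1 (SAP 2.2), and weeks 4 to 12, that is 8 weeks each.
- Stoppers per arm: 92.5 × 0.10 = 9.25
- 9.25 × 8 = 74 patient-weeks; 74 × 7/365.25 = 1.42 patient-years
- Nominal arm time: 92.5 × 24 = 2,220 patient-weeks; 74/2,220 = 3.3%
- Assumed withdrawal of 5% to 20%: 0.71 to 2.84 patient-years, 1.7% to 6.7%

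**6. Infections in that time, at Protocol 1.4 NMOSD rates (for scale only).**

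| Rates used | Satralizumab | Placebo |
|---|---|---|
| Add-on study | 1.42 × 1.325 = 1.9 | 1.42 × 1.496 = 2.1 |
| Monotherapy study | 1.42 × 0.998 = 1.4 | 1.42 × 1.626 = 2.3 |

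For comparison, 24 weeks in one arm is 2,220 × 7/365.25 = 42.5 patient-years, or about 56 infections at 132.5 per 100.

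**7. What the follow-up set contains under the SAP's grouping rule.**

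| Stopper | Taking when stopped | Labelled |
|---|---|---|
| DB, satralizumab | satralizumab | satralizumab |
| DB, placebo | placebo | placebo |
| OLE, formerly satralizumab | satralizumab | satralizumab |
| OLE, formerly placebo | satralizumab | placebo |

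The placebo column mixes drug-free and drug-exposed follow-up, and both columns mix randomised with open-label time.

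**The case against.** The other side has several good points.

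- **Nothing is dropped.** A reader might infer that late events vanish. They do not: the SAP defines a set for them, and SAP 4.1 presents results by arm as a general rule. This stands as to loss. It does not supply the comparison, because of the pooling and labelling in step 7.
- **Near-full drug effect is not shown.** A reader might carry the occupancy figure above 95% across weeks 5 to 12. It is a model-predicted NMOSD median on continued dosing, and it applies at the last included day. Anti-drug antibodies, seen in 41% and 71% of satralizumab patients in the two NMOSD studies, went with lower exposure, and early stoppers may not have reached steady state. The remark about several months' persistence comes from sections on CYP substrates. All of this stands.
- **No favour to satralizumab is shown.** The window is the same in both arms, and the NMOSD infection rates are higher on placebo, so slightly more placebo infections would move out. Removing events together with their person-time leaves a rate unchanged unless risk differs in that period, which is not shown. This stands.
- **Stopping often for neutropenia, liver enzymes or infection is not documented.** Much of the protocol's guidance is to interrupt, and interrupted participants stay in the main tables. This stands.
- **Four weeks is coherent.** It gives discontinuers the same post-dose window as completers who enter the OLE. Someone counted to 12 weeks may also have moved to another therapy. This is a fair reason to keep the 4-week window as the main analysis.

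**Conclusion.** The point holds in a limited form. For permanent discontinuers, no planned by-arm table covers the protocol's own 12-week adverse event reporting period, and the follow-up set as defined cannot stand in for one. The amount is small: at most about 1.4 patient-years per arm, 3.3% of arm time, and about two infections in each arm on borrowed add-on rates. The documents do not support a claim that the result is biased towards satralizumab, or that the excluded events all occur under near-full receptor blockade. What remains is that a rare death or serious event in a discontinuer could be missing from the randomised comparison.

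The size rests on the plan's 10% withdrawal rate, equal stopping in the two arms, the full eight weeks being observed (last contact or the clinical cut-off may shorten it), and NMOSD infection rates applied to gMG.

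**What to change.** Keep the 4-week while-on-treatment set as the main analysis. In SAP 4.5 and 4.5.2:

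1. Add supportive DB tables of deaths, SAEs, infections and AESIs by randomised arm, running to 12 weeks after the last DB dose and capped at the first OLE dose, last contact or the clinical cut-off.
2. Split the safety follow-up set into DB stoppers and OLE stoppers, and label each participant by the treatment being taken when stopped.

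The data are already collected, so the cost is SAP wording, one window setting and two or three extra tables. The downside is that those tables include some low-exposure time and possibly events after a switch to other therapy. A footnote saying so, with the 4-week tables beside them, deals with that.
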